7.3.1 Time course

Baseline Evaluation (day 0):

• 2 faecal samples collected within 48 hours prior to Beta-glucan intake for analysis of microbiota. Blood sampling prior to Beta-glucan intake for immunological analysis (cytokine production of leukocytes stimulated *ex vivo* with various stimuli), for analysis of peripheral blood mRNA expression of genes related to the immune response, epigenetic modifications, levels of Beta-glucan, and phagocytosis and killing of *C. albicans*.

3 hours after the first Beta-glucan intake (day 0 + 3 hours):

• Blood sampling for immunological analysis (cytokine production of leukocytes stimulated *ex vivo* with various stimuli), for analysis of peripheral blood mRNA expression of genes related to the immune response, and levels of Beta-glucan.

6 hours after the first Beta-glucan intake (day 0 + 6 hours):

• Blood sampling for immunological analysis (cytokine production of leukocytes stimulated *ex vivo* with various stimuli), for analysis of peripheral blood mRNA expression of genes related to the immune response and levels of Beta-glucan.

24 hours after the first Beta-glucan intake (day 1):

• Blood sampling for immunological analysis (cytokine production of leukocytes stimulated *ex vivo* with various stimuli), for analysis of peripheral blood mRNA expression of genes related to the immune response and levels of Beta-glucan.

Days 0-5:

• Daily intake of 1000mg Beta-glucan

Day 6:

- 1 faecal sample collected within 24 hours prior to the last Beta-glucan intake for analysis of microbiota. Blood sampling prior to the last Beta-glucan intake for immunological analysis (cytokine production of leukocytes stimulated *ex vivo* with various stimuli), for analysis of peripheral blood mRNA expression of genes related to the immune response, epigenetic modifications, levels of Beta-glucan, and phagocytosis and killing of *C. albicans*.
- Registration of any adverse experience. This includes any intercurrent illness that may arise during therapy.

3 hours after the last Beta-glucan intake (day 6 + 3 hours):

• Blood sampling for immunological analysis (cytokine production of leukocytes stimulated *ex vivo* with various stimuli), for analysis of peripheral blood mRNA expression of genes related to the immune response, levels of Beta-glucan.

6 hours after the last Beta-glucan intake (day 6 + 6 hours):

• Blood sampling for immunological analysis (cytokine production of leukocytes stimulated *ex vivo* with various stimuli), for analysis of peripheral blood mRNA expression of genes related to the immune response and levels of Beta-glucan.

Day 21:

- 1 faecal sample collected within 24 hours prior to the last Beta-glucan intake for analysis of microbiota. Blood sampling for immunological analysis (cytokine production of leukocytes stimulated *ex vivo* with various stimuli (including LPS, peptidoglycan, candida), and for analysis of peripheral blood mRNA expression of genes related to the immune response, epigenetic modifications, and levels of Beta-glucan.
- Registration of any adverse effects. This includes any intercurrent illness that may arise during the study period.

7.3.2 Laboratory tests

Immunological sampling

- Time-points: days 0, 0+3hrs, 0+6hrs, 6, 6+3hrs, 6+6hrs, and 21
- Parameters to be tested:
 - Ex-vivo cytokine production;
 - After 24h stimulation, determination of TNF-α, IFN-1, IL-6, IL-1β.
 - After 48h stimulation, determination of IL-10, IFN-γ
 - After 7 day stimulation, determination of IL-17 and IL-22
 - Method: PBMC and monocyte stimulation. Stimuli to be used: RPMI (control stimuli), LPS, Pam3Cys, Poly(I:C), C. albicans, staphylococcus aureus, and mycobacterium tuberculosis.
 - o Peripheral blood mRNA expression of genes related to the immune response
 - Peripheral blood levels of Beta-glucan
 - Epigenetic modifications
 - phagocytosis and killing of *C. Albicans*
 - Faecal microbiota
- Total amount of blood needed: 360ml (45 ml on 8 different timepoints)
 - o 40 ml EDTA-anticoagulated blood for stimulation experiments, phagocytosis/killing, and epigenetic analysis.
 - 2.5 ml collected directly into a PAXGene[®] Blood RNA tubes (PreAnalytix). These tubes are used to prevent any post-sampling stimulation and to ensure RNA integrity after storage. The reagents used in these BD VacutainerTM tubes allow immediate nucleic acid precipitation and nuclease inhibition. After collection and RNA stabilization at room temperature (4 hours), samples are stored at -20°C until RNA extraction.
 - o 2 ml heparin anticoagulated blood for determination of Beta-glucan by ELISA

In order to take into account the value of the biological samples obtained during this study, all leftovers will be stored in a biobank at the end of the study. This includes (if available) whole

blood, serum, plasma, RNA for the duration of 5 years. Those samples will be secondarily used for research in the field of sepsis or related pathologies. Each participant in the study will be appropriately informed and will have the right to refuse the storage of his/her own samples.

7.3.3 Methods of determination

All blood sampling will be performed on blood obtained by venapuncture. Approximately 8 x 45 ml blood will be obtained (before, and 3, 6, and 24 hours after the first Beta-glucan ingestion (day 0), before, and 3 and 6 hours after the 7th ingestion of Beta-glucan (day 6), and on day 21), with a maximum of 360 ml throughout the whole study (see appendix 1 for flowchart).

Ex vivo leukocyte stimulation will be performed at the Laboratory of Experimental Internal Medicine of the Radboud University Nijmegen Medical Centre. Cytokines in supernatants of stimulated leukocyte cultures will be determined by ELISA. At this laboratory ELISA for determination of Beta-Glucan will be performed as well.

Transcriptional activity of leukocytes will be determined by RNA sequencing at the Department of Genetics of the Radboud University Nijmegen Medical Centre. Transcriptomics analysis, systems biology, and microbiota analysis will be performed in collaboration with the group of [name], Harvard University and Broad Institute at MIT.

Changes in phenotype or gene expression caused by mechanisms other than changes in the underlying DNA sequence (epigenetics) will be determined by ChIP assays at the Laboratory of Experimental Internal Medicine of the Radboud University Nijmegen Medical Centre in cooperation with the Department of Molecular Biology of the Nijmegen Centre for Molecular Life Sciences.

Analysis of phagocytosis and killing will be determined by a phagocytosis and killing assay performed at the Laboratory of Experimental Internal Medicine of the Radboud University Nijmegen Medical Centre.

7.4 Withdrawal of individual subjects

Subjects can withdraw from the study at any time without any consequences and without the need to give an explanation if they wish to do so. The investigator can decide to withdraw a subject from the study for medical reasons. Subjects that withdraw during the study will receive a proportional fee.

7.4.1 Specific criteria for withdrawal

When the subject has given informed consent, the subject is irrevocably admitted to the trial. Even if the subject is withdrawn from receiving further medication, documentation according to the study protocol must be as complete as possible.

A patient can or will be withdrawn from the study:

- upon request of the subject
- after protocol violation
- at the discretion of the investigator

7.5 Replacement of individual subjects after withdrawal

After withdrawal or exclusion of a subject, he will be replaced to maintain adequate power of the study. Maximum 10 subjects will be replaced.

7.6 Follow-up of subjects withdrawn from treatment

For all subjects who are prematurely withdrawn from treatment, the reason will be documented carefully. The patients who had a dose of Beta-glucan will at least be included in the safety evaluation. For all subjects who were withdrawn after randomization, but before Beta-glucan administration, the reason why will be documented.

7.7 Premature termination of the study

The coordinating investigators have the right to discontinue the clinical study at any time for medical or procedural reasons.

SAFETY REPORTING

7.8 Section 10 WMO event

In accordance to section 10, subsection 1, of the WMO, the investigator will inform the subjects and the reviewing accredited METC if anything occurs, on the basis of which it appears that the disadvantages of participation may be significantly greater than was foreseen in the research proposal. The study will be suspended pending further review by the accredited METC, except insofar as suspension would jeopardise the subjects' health. The investigator will take care that all subjects are kept informed.

7.9 Adverse and serious adverse events

7.9.1 Adverse event

Adverse events are defined as any undesirable experience occurring to a subject during a clinical trial, whether or not considered related to the investigational drug. All adverse events reported spontaneously by the subject or observed by the investigator or his staff will be recorded.

7.9.2 Serious Adverse Events

A serious adverse event is any untoward medical occurrence or effect that at any dose:

- results in death;
- is life threatening (at the time of the event);
- requires hospitalisation or prolongation of existing inpatients' hospitalisation;
- results in persistent or significant disability or incapacity;
- is a congenital anomaly or birth defect;

- is a new event of the trial likely to affect the safety of the subjects, such as an unexpected outcome of an adverse reaction, lack of efficacy of an IMP used for the treatment of a life threatening disease, major safety finding from a newly completed animal study, etc.

All SAEs will be reported to the accredited METC that approved the protocol, according to the requirements of that METC.

7.9.3 Suspected unexpected serious adverse reactions (SUSAR)

Adverse reactions are all untoward and unintended responses to an investigational product related to any dose administered.

Unexpected adverse reactions are adverse reactions, of which the nature, or severity, is not consistent with the applicable product information (e.g. Investigator's Brochure for an unapproved IMP or Summary of Product Characteristics (SPC) for an authorised medicinal product).

The sponsor will report expedited the following SUSARs to the METC:

- SUSARs that have arisen in the clinical trial that was assessed by the METC;
- SUSARs that have arisen in other clinical trial of the same sponsor and with the same medicinal product, and that could have consequences for the safety of the subjects involved in the clinical trial that was assessed by the METC.

The remaining SUSARs are recorded in an overview list (line-listing) that will be submitted to the METC. This line-listing provides an overview of all SUSARs from the study medicine, accompanied by a brief report highlighting the main points of concern.

The sponsor will report expedited all SUSARs to the competent authority, the Medicine Evaluation Board and the competent authorities in The Netherlands.

The expedited reporting will occur not later than 15 days after the sponsor has first knowledge of the adverse reactions. For fatal or life threatening cases the term will be maximal 7 days for a preliminary report with another 8 days for completion of the report.

7.10 Follow-up of adverse events

All adverse events will be followed until they have abated, or until a stable situation has been reached. Depending on the event, follow up may require additional tests or medical procedures as indicated, and/or referral to the general physician or a medical specialist.

7.11 Data Safety Monitoring Board (DSMB)

A DSMB is established for this study to perform ongoing safety surveillance and to perform interim analyses on the safety data. the DSMB is an independent committee completely unblinded for treatment allocation and is composed of the following persons:

[name], anaesthesist Radboud University Nijmegen Medical Centre Department of Anesthesia, [name]

[name], internist-pharmacologist Radboud University Nijmegen Medical Centre Department of Pharmacology & Toxicology, [name]

One interim analysis will be performed after 7 subjects have completed the study. A DSMBcharter is attached (ATTACHMENT 1). The interim analysis will focus on the following issues: adverse events: type, severity, duration, action taken and attributability to Beta-glucan intake.

The following criteria are defined on which basis the DSMB may decide to terminate the trial prematurely:

• Any serious adverse Event

7.12 Abnormal laboratory tests results

The results of all laboratory tests required by the protocol will be recorded in the subjects case record form. All clinically important abnormal laboratory tests occurring during the study will be repeated at appropriate intervals until they return either to baseline or to a level deemed acceptable by the investigator, or until a diagnosis that explains them is made.

8 STATISTICAL ANALYSIS

8.1 Modified intention to treat analysis

Not applicable.

8.2 Descriptive statistics

For the descriptive statistics, values will be given as mean \pm SD or median and ranges, depending on their distribution. For comparisons, paired Students t -tests or Willcoxon-tests for parametric and nonparametric data as appropriate will be used. Changes over time will be analysed using ANOVA repeated measures. A p value <0.05 is considered significant. Statistical analyses will be performed with SPSS 16.0 (SPSS, Chicago, IL) software.

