Drugs and dosage Commercial available Beta-glucan derived from bakers yeast (S. Cerevisiae): Glucan #300® produced by Transferpoint, Columbia, United States. 2 capsules of 500mg Glucan #300®, daily, for seven days.

Route of administration Oral administration.

Procedures 10 Healthy volunteers will take Beta-glucan 1000 mg daily for seven days, 5 other healthy volunteers will serve as a control group and do not have to take Beta-glucan. The *ex-vivo* responsiveness of leukocytes to various inflammatory stimuli, peripheral blood mRNA expression of genes related to the immune response, epigenetic modifications, the leukocyte capacity to phagocytose and kill the fungal pathogen *Candida albicans*, blood levels of Beta-glucan, and faecal microbiota will be analyzed on different timepoints.

Statistical analysis Descriptive statistics.

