3 STUDY DESIGN

An open-label, intervention pilot-study in 15 healthy human volunteers. In this pilot study, we will enrol 10 subjects who will take Beta-glucan daily for seven days, and 5 subjects who will serve as control group and do not have to take Beta-glucan but who will be analyzed at the same time points as the subjects in the Beta-glucan group.

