7.1.3 Other study parameters Not applicable

7.2 Randomisation, blinding and treatment allocation

We will use a open-label design in which subjects will be randomized to the Beta-glucan or control group by the opening of sealed envelopes.

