8.3 Multivariate analysis

Not applicable.

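### Section 8.2 names only paired tests for comparisons and states no group term, so no named analysis uses the randomised 10 v 5 contrast

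*Protocol*

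**What the plan says.** Protocol section 3 sets up two concurrent groups: "we will enrol 10 subjects who will take Beta-glucan daily for seven days, and 5 subjects who will serve as control group". It adds that the controls are measured on the treated subjects' schedule. Section 7.2 makes this a randomised parallel design: "subjects will be randomized to the Beta-glucan or control group by the opening of sealed envelopes". Section 7.1.1 names the primary outcome, TNF-alpha secretion by LPS-stimulated PBMCs.

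Section 8.2 then fixes the tests: "For comparisons, paired Students t -tests or Willcoxon-tests for parametric and nonparametric data as appropriate will be used". It continues: "Changes over time will be analysed using ANOVA repeated measures". The threshold is set there too: "A p value <0.05 is considered significant". Section 8.3 offers nothing further: "8.3 Multivariate analysis Not applicable". Nowhere does section 8 name an unpaired t-test, a rank-sum test, a group factor, a group-by-time interaction or a baseline-adjusted group difference.

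**The concern.** A paired test compares a subject with himself. Ten treated subjects and five controls are different people in groups of unequal size, so they cannot be paired. The test family that section 8.2 assigns to comparisons therefore does not fit the design in sections 3 and 7.2.

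The outcome is an ex vivo stimulation assay repeated from day 0 to day 21. Time of day, repeated venepuncture and assay run can all move it in both arms alike. The control arm is there to remove such shared movement. A within-arm test leaves it in the result, where it looks the same as a Beta-glucan effect. At stake is whether a significant primary result can be attributed to Beta-glucan at all.

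**Working it through.** **Inputs.** From the protocol: 10 treated and 5 controls (section 3), and a significance threshold of 0.05 (section 8.2; two-sided is assumed, since sidedness is not stated). Section 4.4 declines a power calculation, and no SD, effect size or drift is given. There is therefore no plan figure to reproduce. Drift is an assumption, shown as a range in units of the SD of within-subject change.

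**Step 1: what each test estimates.** Let the true Beta-glucan effect on change be b and the shared drift be d.
- Paired test in the treated arm: expected mean change = b + d.
- Between-arm test of change: (b + d) − d = b.

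Only the second isolates b, whatever the value of d.

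**Step 2: false positives when b = 0.** With d in SD units, the paired t-test rejects with probability P(|T| > t), where T is non-central t on n − 1 degrees of freedom with non-centrality d√n. At n = 10 and d = 0.5 the non-centrality is 0.5 × 3.162 = 1.58, which gives 0.293. At n = 5 it is 0.5 × 2.236 = 1.12, which gives 0.141. The arms are independent, so treated significant with control not significant has probability p10 × (1 − p5).

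| Shared drift (SD) | Treated arm significant (p10) | Control arm significant (p5) | Treated yes, control no |
|---|---|---|---|
| 0 | 0.05 | 0.05 | 0.05 |
| 0.25 | 0.109 | 0.072 | 0.101 |
| 0.5 | 0.293 | 0.141 | 0.252 |
| 0.75 | 0.562 | 0.254 | 0.419 |
| 1.0 | 0.803 | 0.401 | 0.481 |
| 1.5 | 0.987 | 0.711 | 0.286 |

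Example: 0.803 × (1 − 0.401) = 0.481.

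**Step 3: the between-arm test under the same conditions.** In simulation (20,000 runs), an unpaired t-test of change, 10 v 5, rejected in 0.052 / 0.051 / 0.051 of trials at drift 0 / 0.5 / 1.0 SD.

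**Step 4: the repeated-measures ANOVA.** In simulation (5,000 runs, 8 times, linear drift, subject effect plus independent noise), the time effect within the treated arm was significant in 0.05 / 0.24 / 0.84 of trials at drift 0 / 0.5 / 1.0 SD. The group-by-time term was significant in 0.050 / 0.052 / 0.055. The ANOVA that section 8.2 already names is thus sound against shared drift if its group-by-time term is used, and not if only time is tested.

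**Step 5: rank tests.** The smallest exact two-sided signed-rank p with n = 5 is 2/2^5 = 0.0625, above the threshold. The smallest exact rank-sum p for 10 v 5 is 2/C(15,5) = 2/3003 = 0.0007.

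**Step 6: price of the right contrast.** For the 10 v 5 t-test the non-centrality is D/√(1/10 + 1/5) = D/0.548, where D is the true difference in SD of change. Power is 0.39 at D = 1.0 and 0.72 at D = 1.5, and reaches 0.80 at D = 1.66. The paired test with n = 10 reaches 0.80 at 1.00 SD.

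**The case against.** The best defence is that section 8.2 is brief rather than wrong. A repeated-measures ANOVA can carry a group factor, the Wilcoxon name also covers the rank-sum test, and model terms are often left to a statistical analysis plan. Section 7.3 also asks some questions within subjects, such as whether repeated intake adds to the first-day effect, and paired tests are natural there. Finally, this is a pilot with no power calculation.

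Part of this stands. A reader might infer that the arms will never be compared; the text supports only that no between-group test is named. But the sentence on comparisons opens with the word paired, and the ANOVA is tied only to time. The protocol is not silent: it names a test family that cannot make the comparison its design was built for. Even the within-subject questions concern a Beta-glucan effect, so shared drift still has to be removed. Pilot status excuses low power, not tests that bypass the control arm.

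Three stronger readings should be resisted:
- **That controls are certain to be non-significant.** The 0.0625 floor applies only to the exact signed-rank test. The protocol does not say exact or asymptotic. The normal approximation gives 0.043 for the same most extreme result (z = 7.5/√13.75 = 2.02), and the paired t-test can also reach p<0.05 with five subjects.
- **That unequal arm sizes cause the side-by-side fallacy.** They worsen it. With 10 per arm the pattern would still occur in 0.293 × 0.707 = 21% of trials at 0.5 SD and 0.803 × 0.197 = 16% at 1.0 SD, against 25% and 48% here. Nor does the protocol say that conclusions will rest on such a contrast.
- **That the synopsis contradicts section 8.2.** Its entry, "Statistical analysis Descriptive statistics", repeats the title of section 8.2, under which the tests sit, and is better read as shorthand.

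**Conclusion.** The point holds: section 8.2 is wrong as written, not merely short of detail. It assigns paired tests to comparisons in a randomised parallel trial, and no analysis it names is stated to use the randomised contrast. Within-arm results, taken alone or set side by side, cannot separate shared drift from a Beta-glucan effect.

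The size is conditional. The 29% and 80% false-positive rates in the treated arm, and the 25% and 48% for the side-by-side pattern, assume shared drift of 0.5 and 1.0 SD with normally distributed changes. They illustrate the problem and are not properties of this trial; with no drift the paired test holds its 5%. The direction does not depend on the drift chosen, because shared drift cancels only in the between-arm difference.

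**What to change.** Reword section 8.2 as follows:
- **Primary comparison:** the between-group difference in change of LPS-stimulated TNF-alpha from the day-0 pre-dose value, at one time point named in advance.
- **Method:** ANCOVA adjusted for the pre-dose value, or the group-by-time term of the repeated-measures model already named.
- **Sensitivity analysis:** an exact rank-sum test of change, 10 v 5.
- **Reporting:** the estimated difference with a 95% CI. Within-arm paired results stay as description only.

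This needs no new subjects, samples or assays. The cost is precision: 80% power requires a difference of about 1.66 SD of change, against 1.00 SD for the paired test in ten subjects. That is acceptable in a pilot that makes no power calculation, and the confidence interval will show the uncertainty.

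### Section 8.2's within-arm tests at p<0.05 give verdicts that cannot be compared between 5 controls and 10 treated subjects; a two-sided signed-rank test in the controls can barely, or never, be significant

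*Protocol*

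**What the plan says.** Protocol section 8.2 gives the whole testing rule in a few lines:

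- Choice of test: for comparisons, paired t-tests or "Willcoxon-tests for parametric and nonparametric data as appropriate will be used".
- Time course: "Changes over time will be analysed using ANOVA repeated measures".
- Threshold: "A p value <0.05 is considered significant".
- Software: "Statistical analyses will be performed with SPSS 16.0 (SPSS, Chicago, IL) software".

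Section 3 fixes the arms: "we will enrol 10 subjects who will take Beta-glucan daily for seven days", and "5 subjects who will serve as control group". The controls are people "who will be analyzed at the same time points as the subjects in the Beta-glucan group". Section 7.2 allocates subjects to the two arms at random, so the groups are parallel and each person belongs to one arm only. Section 7.5 replaces withdrawn subjects, so five controls is the intended number. Section 4.4 gives no power calculation.

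Section 8.2 does not say whether tests are one- or two-sided, whether Wilcoxon p-values are exact or approximate, or in which arm the paired tests are run. It names no comparison of change between the arms.

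**The concern.** The controls follow the same sampling schedule so that drift over three weeks (assay, diet, time of day) can be told apart from an effect of Beta-glucan. In a parallel trial a paired test compares a subject with himself, so the tests named for comparisons naturally become one before/after test per arm. The reader then sets two verdicts side by side.

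That reading is safe only if the test can respond in both arms. With five pairs, a signed-rank test has so few possible outcomes that 0.05 lies at or beyond the edge of what it can produce. With ten pairs it has ample room. The combination of treated significant and control not significant can then arise from the arm sizes alone. It would be taken as a drug effect on the primary outcome, LPS-stimulated TNF-alpha, and on any other cytokine sent to the Wilcoxon branch.

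**Working it through.** The protocol states no minimum p-value, power or effect size, so there is no figure of its own to reproduce.

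**Inputs.** Threshold p<0.05 (8.2); 5 controls and 10 treated (section 3). Assumptions: two-sided testing, differences with no ties and no zeros, Wilcoxon read as the paired signed-rank test.

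**Step 1: minimum p in the controls.** Under no change, each of the 2^5 = 32 sign patterns is equally likely. The most extreme result is all five differences in one direction, which gives rank sum W = 15.

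- Exact, two-sided: 2/32 = 0.0625.
- Normal approximation, uncorrected: mean 5×6/4 = 7.5; variance 5×6×11/24 = 13.75; z = 7.5/√13.75 = 2.02; p = 0.043.
- With continuity correction: z = 7.0/√13.75 = 1.89; p = 0.059.
- Next most extreme pattern (W = 14), uncorrected: z = 6.5/√13.75 = 1.75; p = 0.080.

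The exact and corrected versions therefore have no outcome below 0.05. The uncorrected version has only the all-same-direction outcome, whose true probability under no change is 2/32 = 6.25%, above the stated 5%.

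**Step 2: minimum p in the treated arm.** Exact, two-sided: 2/2^10 = 2/1024 = 0.002. The smallest arm in which the exact two-sided test can fall below 0.05 is six subjects (2/64 = 0.031).

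**Step 3: how often a shared change looks like a drug effect.** Suppose both arms change by the same amount, in SD units of the change, and Beta-glucan does nothing. The arms are independent, so

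P(treated significant, control not) = P(treated significant) × [1 − P(control significant)].

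For the paired t-test with normal changes, each probability comes from the noncentral t distribution with n − 1 degrees of freedom and noncentrality d√n:

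| Shared change d | Treated, n = 10 | Control, n = 5 | Treated significant, control not |
|---|---|---|---|
| 0.5 SD | 0.293 | 0.141 | 0.293 × 0.859 = 25% |
| 1 SD | 0.803 | 0.401 | 0.803 × 0.599 = 48% |
| 1.5 SD | 0.987 | 0.711 | 0.987 × 0.289 = 29% |

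With signed-rank tests on the same simulated normal changes, the last column becomes 28%, 78% and 98% if exact p-values are used in both arms. It becomes 24%, 45% and 29% if the uncorrected approximation is used in the controls. These signed-rank figures only illustrate the size of the problem, because 8.2 would send normal data to the t-test.

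**Step 4: a comparison that does respond.** An exact two-sided rank-sum test on the changes of all 15 subjects has 15!/(10!×5!) = 3003 equally likely allocations. Its smallest p is 2/3003 = 0.0007. Under a shared change its error rate stays at or below 5%.

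**The case against.** A reader might infer that the control arm must return no significant change whatever its data show. The document does not support that, for four reasons.

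- Section 8.2 fixes neither sidedness nor the type of p-value. An exact one-sided test can reach 1/32 = 0.031, and the uncorrected approximation can reach 0.043.
- The same section names the paired t-test and repeated-measures ANOVA, and both can be significant with five subjects. Differences of 1, 2, 3, 4 and 5 give a t-test p of 0.013.
- Section 8.2 does not prescribe a separate test in the controls. That is inferred from the word paired and from the shared time points. If the Wilcoxon test were meant as the unpaired rank-sum test, the minimum would be 0.0007.
- Most of the false contrast at small shared changes is not due to the Wilcoxon floor. At 0.5 SD the t-test already gives 25% against 28% for the exact signed-rank test.

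One can add that this is a pilot without a power calculation, that the synopsis lists the analysis only as descriptive, and that exact versus approximate p-values are often settled in an analysis plan, which may exist unseen.

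All of this limits the claim, but it does not remove it. The test family, the threshold and the arm size are all fixed in the protocol, and on the most natural reading they do not work together. Pilot status excuses low power. It does not make significance verdicts from arms of 5 and 10 comparable, and 8.2 names no between-arm comparison of change to take their place.

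**Conclusion.** The point holds in a limited form. If 8.2 is applied as two-sided before/after tests within each arm, the Wilcoxon branch cannot be significant in the five controls with exact (0.0625) or continuity-corrected (0.059) p-values. Uncorrected, it can be significant on a single pattern, at a true error rate of 6.25%. The treated arm has an exact floor of 0.002. The two verdicts are therefore not comparable, and a change common to both arms can pass for a Beta-glucan effect.

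The broader cause is separate testing in arms of unequal size, which affects the t-test branch too (25%, 48% and 29% at shared changes of 0.5, 1 and 1.5 SD). The Wilcoxon floor adds to this mainly at larger shared changes and only if exact p-values are used.

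The conclusion rests on the within-arm signed-rank reading, two-sided testing and untied differences. The percentages also rest on assumed normal changes of equal size in both arms; the protocol gives no effect size or SD from which to choose among them. It is worth correcting because the remedy is nearly free.

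**What to change.** In section 8.2:

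- Base the conclusion about Beta-glucan on a between-arm comparison of change from the day-0 pre-dose value, using all 15 subjects. Where the changes are non-normal, use an exact two-sided rank-sum test on them.
- Report the control-arm change as an estimate with a 95% confidence interval and no significant/non-significant label. The interval should be t-based, on a transformed scale if needed. One obtained by inverting the exact signed-rank test in five subjects cannot exceed 1 − 0.0625 = 93.75% coverage.
- State that tests are two-sided and that rank-test p-values are exact.

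This costs a few lines of text and no new data, subjects or samples. The small downside is that the control result becomes a wide interval instead of a yes/no label.
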